Comparative Effectiveness of Two State Payer Strategies to Prevent Unsafe Opioid Prescribing

(PCORI UOP-2017C2-8509)

Study Protocol

November 1, 2022

1. Background

Use and misuse of opioids is now recognized as a major U.S. public health problem, leading to significant morbidity and mortality. While most acute pain episodes (0-6 weeks) resolve, some go on to subacute pain (6-12 weeks), and a minority of individuals develop chronic pain (> 3 months). Musculoskeletal (MSK) conditions were among the top 5 conditions contributing to years lived with disability (YLD) in the U.S. between 1990 and 2010. Common MSK conditions are accounting for an increasingly large fraction of long-term work disability in the U.S. Importantly, these are also the patients who have received disproportionate amounts of chronic opioids, accounting for the largest relative costs to Medicare. Prescribing of both opioids and concurrent sedative-hypnotics for acute and chronic MSK pain increased dramatically from 2001 to 2010.

The body of evidence to date suggests that, among individuals with non-cancer pain: (1) even short-term opioid use early after injury is associated with greater risk of long-term opioid use and disability; (2) opioid use poses risks of serious harms, including overdose death, particularly when prescribed at high doses and/or concurrently with sedative-hypnotic medications; and (3) evidence is lacking concerning effectiveness of long-term opioid therapy for chronic pain. The clearest path to preventing transition to chronic opioid use and associated morbidity or addiction is to reduce unnecessary prescribing during the acute and subacute phases of pain.

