Aim 3 patient in-depth interviews. Patients who had an opioid prescription for at least 6 weeks paid for by WC or whose prescription payments have been reviewed in accordance with the state's ORP.

Exclusion Criteria

Aims 1, 2, & 3 (patient in-depth interviews only). Injured workers who are under 18 years of age.

Aims 1 & 2. Current cancer diagnosis and (for surveys only) non-English or -Spanish speakers, physically or mentally incapable of completing the survey, incarcerated, or deceased.

Aim 3. Non-English speakers.

Number of Study Groups/Cohorts

The primary analysis involves 2 groups/cohorts of injured workers, 1 from WA and 1 from OH. Secondary analyses involve two subgroups of injured workers within WA, defined by whether the injured worker's attending provider participates in Centers of Occupational Health and Education (COHE) care delivery.

Enrollment/Sample Size

Aims 1 & 2. The time series for Aim 1 will be based on data for all injured workers in OH and WA who file a new State Fund claim from January 1, 2010 through December 31, 2020. For the prospective cohort analysis, we anticipate including 4,636 eligible workers in WA and 779 in OH for a one-year cohort. Using WC claims, pharmacy billing data, and potentially prescription drug monitoring program (PDMP) data from each state, we will track opioid prescribing for each injured worker for a full year after date of injury. The worker survey will largely be drawn from this cohort, depending on the length of time needed to conduct an adequate number of surveys. All workers will be interviewed initially at 4-6 weeks

after injury (baseline). Workers who complete the baseline survey in the first year of recruitment will be asked to complete follow-up surveys at 6- and 12-months after injury. Workers who complete the baseline survey after the first year of recruitment will be asked to *only* do the 6-month follow-up survey due to time constraints. We anticipate that roughly 3,120 workers in WA and 525 workers in OH will complete baseline surveys. We anticipate roughly 1,700 completed 12-month outcome surveys from WA and 234 from OH.

Aim 3 key informants. No more than 12 interviews in WA, supplemented with policy documents to add detail. In OH, we will start with policy documents and use key informant interviews with individuals outside of BWC to complement and supplement the historical account.

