Surveys will be conducted at approximately 6 weeks (baseline), 6 months, and 12 months after injury. We anticipate that roughly 3,120 workers in WA and 525 workers in OH will complete baseline surveys. Based on estimated response rates, we anticipate roughly 1,700 completed 12-month outcome surveys from WA and 234 from OH. Depending on survey eligibility and response rates, up to 100% of survey

respondents may be drawn from the underlying WA/OH cohorts (however, it is possible that survey accrual may need to continue beyond cohort accrual).

The primary predictor is binary (1 for WA cases, 0 for OH cases). We will specify GEE panel models as described for Analysis Topic B to account for outcome measures at multiple time points for each patient (6 months, 12 months). Appropriate GEE link functions will be specified for each outcome variable, e.g., identity link for continuous variables, logit link for binary variables, and log link for counts (Tables 2 and 3). Comparisons of clinically important improvements in patient pain and functioning will be based on the proportion of patients who achieve clinically meaningful improvement (relative to baseline) on our outcome measures at 6 and 12 months, as defined by 30% or greater improvement. We will include time/state interactions in order to assess (1) change in outcomes over time and (2) differences in such changes by state.

Covariates described under Analysis Topic B will also be included for this analysis, in addition to baseline covariates collected during the survey. Additional survey-based covariates will include the following (this list may be adjusted as the survey is finalized with stakeholder input):

- Education
- Household Income
- Race/ethnicity
- Health status
- Comorbidities (survey-based FCI, current cancer treatment)
- Pain intensity
- Physical function/pain interference
- Emotional functioning-Anxiety
- Emotional functioning-Mood
- Quality of life
- Work status and barriers to work
- Treatment for pain
- Satisfaction with treatment
- Communication with health care provider
- Alcohol and tobacco use

Using these covariates, we will calculate a propensity score. In order to minimize the loss of survey data, we plan to include this propensity score in the causal models along with important covariates. However, if needed to achieve balance on baseline variables, we will restrict the analytic sample to the region of common support and/or implement propensity score matching.

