This analysis is focused on the secondary and exploratory patient outcomes for this study, using administrative and survey data for the WA survey sample. Surveys will be conducted at approximately 6 weeks (baseline), 6 months, and 12 months after injury. Our estimates are rough and will be updated as survey enrollment proceeds. However, we anticipate that roughly 3,120 workers in WA will complete baseline surveys, that roughly 1,700 will completed 12-month outcome surveys, and that approximately half of those interviewed will have an attending provider affiliated with COHE.

This analysis will test Hypothesis 2A (stated above) with respect to patient outcomes, using parallel analyses to those described in Analysis Topic H. Most secondary and exploratory patient outcomes will be based on survey data, but several will be based on WC data (see Tables 2 and 3). The only adjustments to Analysis Topic H are that models will include only the WA survey sample, and the binary primary predictor and propensity score calculations will be based on COHE status rather than on state jurisdiction (1 for COHE, 0 for non-COHE).

Additional Information Relevant to Quantitative Analyses for Aims 1, 2, and 2A

Subgroups of Interest

Planned subgroup analyses are listed under the relevant analysis topics above. Because all subgroup analysis will be exploratory, non-exhaustive examples of potential subgroups have been specified. New subgroups of interest may be identified via exploratory data analysis and/or proposed ad hoc by the principal investigator, co-investigators, or stakeholders. The total number of subgroup analyses—and all subgroups and outcomes analyzed—will be reported, along with subgroup definitions and procedures used. If indicated, multiple comparisons will be accounted for using p-value adjustment.

Operational Definitions for Eligibility Criteria

These definitions will need to be aligned as much as possible across the two states. The following operational definitions are based on our history of working with WA WC data. They may need to be modified after preliminary OH WC data are available for inspection.

- Inclusion criteria:
 - New State Fund claim: Identified by each state WC agency
 - At least one opioid prescription during the first 6 weeks after date of injury: Based on WC pharmacy billing data
 - Ability to speak English or Spanish (for the survey only): This will be determined by interviewers during the contact/consent process
- Exclusion criteria:

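### The 30% responder rule for pain and function sets no minimum score at its week 4-6 baseline, so unequal early recovery between groups would bias the responder comparison

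*Combined protocol and SAP*

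**What the plan says.** Section 7, Analysis Topic H, bases the comparison of clinically important change in pain and function on this measure: "proportion of patients who achieve clinically meaningful improvement (relative to baseline) on our outcome measures at 6 and 12 months, as defined by 30% or" more. These are secondary outcomes (Table 2, PEG-3).

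Baseline is the first survey. Section 4 (Enrollment/Sample Size) says "All workers will be interviewed initially at 4-6 weeks" after injury, and Topic H says "Surveys will be conducted at approximately 6 weeks (baseline), 6 months, and 12 months after injury".

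Under section 4, entry needs an accepted claim and one opioid fill in the first 6 weeks. No inclusion or exclusion criterion concerns the level of pain or function at the survey. Section 1 (Background) reads "While most acute pain episodes (0-6 weeks) resolve, some go on to subacute pain (6-12 weeks", so some low baseline scores should be expected.

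Topic H also plans:

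- identity-link GEE models for continuous outcomes;
- covariates that include baseline pain intensity and physical function;
- a propensity score entered as a covariate;
- restriction to common support, or matching, if balance requires it.

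Topic J applies the same methods to COHE versus non-COHE, "using parallel analyses to those described in Analysis Topic H".

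**The concern.** A percentage improvement needs something to improve from. A worker with a score of 0 at weeks 4-6 cannot fall by 30%, so a worker who has recovered and stays recovered cannot be a responder. The plan sets no floor for the baseline score and no scoring rule for such workers.

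Taken literally, they stay in the denominator as non-achievers. If they were instead treated as missing, the multiple imputation planned for survey outcomes (section 7, Missing Data) would fill in a response that cannot occur. If they were dropped, the denominator would change by an unstated rule.

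The literal reading matters most. The group with more workers recovered by baseline gets a lower responder rate even when later recovery is identical. The responder proportion is the plan's stated basis for clinical importance under Hypotheses 2 and 2A, so an imbalance at week 4-6 could be reported as a difference in benefit.

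**Working it through.** The plan gives no expected responder rate, effect size or power for this outcome, so there is no figure to reproduce. The check asks how far the rule can move the comparison when the two states do not differ in later recovery.

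**Inputs.** From the documents: the 30% threshold, baseline at 4-6 weeks, no minimum score, and about 1,700 (WA) and 234 (OH) completed 12-month surveys. Assumed, because the documents do not give them: the share r at 0 at baseline, the share p of the remaining workers who improve by 30% or more, a 0-10 score, and two-sided 0.05.

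**Formulas.** If workers at 0 count as non-responders and stay well:

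- responder rate = (1 - r) × p
- share doing well at follow-up = r + (1 - r) × p

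**Equal true response, p = 0.50.**

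| r in WA | r in OH | Responders WA | Responders OH | Unadjusted OR (WA vs OH) |
|---|---|---|---|---|
| 15% | 5% | 0.85 × 0.50 = 42.5% | 0.95 × 0.50 = 47.5% | (0.425/0.575)/(0.475/0.525) = 0.82 |
| 10% | 5% | 45.0% | 47.5% | 0.90 |
| 30% | 15% | 35.0% | 42.5% | 0.73 |
| 5% | 15% | 47.5% | 42.5% | 1.22 |
| 20% | 20% | 40.0% | 40.0% | 1.00 |

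The last two rows matter as much as the first three. The bias changes sign when Ohio has more early recovery, and it vanishes when early recovery is equal.

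**The sign can reverse.** With p = 0.60 and 30% (WA) versus 20% (OH) at 0, responders are 0.70 × 0.60 = 42% versus 0.80 × 0.60 = 48% (OR 0.78). Those doing well are 0.30 + 0.42 = 72% versus 0.20 + 0.48 = 68%. At 1,700 and 234 workers, an unadjusted test would find the responder deficit significant about 41% of the time.

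**Effect of the planned covariate.** Large simulations (300,000 workers per state) gave both states identical recovery for a given baseline score and entered that score linearly.

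- With 15% versus 5% at 0 and p = 0.50, the odds ratio moved from 0.82 to about 0.87 (0.86 to 0.88, depending on the assumed baseline distribution).
- With p = 0.60, it moved from 0.78 to 0.87 (20% versus 10% at 0), from 0.79 to 0.90 (30% versus 20%) and from 0.61 to 0.80 (40% versus 20%).
- Excluding zero baselines gave 0.99 to 1.00 in the p = 0.60 scenarios.
- Balancing baseline scores between states gave 1.00 in the 15% versus 5% scenario.

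A linear term therefore reduces the bias without removing it, because response is impossible at 0 and possible everywhere above it.

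**Just above 0.** On a 0-10 integer item (assumed), a one-point drop qualifies from a baseline of 1, 2 or 3. That drop is 100%, 50% and 33% of the score. A 30% change equals a full point only from 1/0.30 = 3.3 upward.

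**The case against.** The strongest reply is that the plan never says recovered workers count as failures. That is correct. A reader might infer such a rule, but change from 0 is undefined and the text is silent. What stands is that the literal wording, a proportion of patients who achieve improvement, leaves these workers as non-achievers. The alternatives would each need a rule the plan does not give.

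Second, the unadjusted odds ratios are not the planned estimate. Topic H adjusts for baseline pain and function, adds a propensity score, and can restrict or match. These steps reduce the bias, and full balance on baseline score would remove it. But matching and common-support restriction are conditional, and linear adjustment leaves a residual.

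Third, a reader might infer that Washington will look worse. The documents give no early-recovery rate for either state, so the direction is open. Different case mix is plausible: the expected cohort is 4,636 of about 93,000 annual accepted claims in WA (5.0%) and 779 of about 90,000 in OH (0.9%). That does not show which state has more workers at 0. The Background sentence on acute pain is general, and gives no share for workers who filled an opioid prescription.

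Fourth, a reader might infer that the rule hides benefit of the state programs gained before baseline. Section 5 does not support this. Washington's payment denial applies beyond six weeks and Ohio's record review takes place at 12 weeks, so a state difference at weeks 4-6 is mainly baseline imbalance.

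Finally, the continuous-score models are already planned and offer a comparison without this defect. That limits the harm but does not repair the responder result.

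**Conclusion.** The point holds in conditional form. The responder rule has no baseline floor. As worded, it makes response impossible for workers already at 0, and it is biased against whichever state has more of them. The size depends on a difference in early recovery that the documents do not report. For differences of 5 to 15 percentage points with 50% true response, the unadjusted odds ratio is 0.73 to 0.90, or the reverse if the imbalance runs the other way. In the 15% versus 5% illustration, linear baseline adjustment leaves about 0.87. With equal early recovery there is no bias. All these figures rest on assumed shares and an assumed 0-10 score. They show what the rule can do and do not forecast the study's result.

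For Topic H the problem is mainly baseline imbalance rather than lost program effect. Topic J differs: section 5 places COHE care in the first 12 weeks, so its week 4-6 baseline lies inside the exposure, and early COHE benefit can count against COHE in the responder rate. These are secondary outcomes, but this rule is how the plan judges clinical importance, so it should be corrected before analysis.

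**What to change.** In Topic H:

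1. Limit the 30% responder analysis to workers at or above a baseline floor fixed before analysis. One option is the score at which 30% equals at least 1 scale point, about 3.3 if the scale is 0-10.
2. Report, by state, the number below the floor and the share of them who stay below it.
3. Interpret the responder result beside the identity-link model of the follow-up score that is already planned.
4. Add a sensitivity analysis in all workers that counts a low follow-up score, defined in advance, as success.

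In Topic J, do not rely on the floor or on baseline adjustment, since either would condition on a score that COHE may already have changed and would remove early benefit. Report follow-up pain and function status in all workers, without adjusting for week 4-6 pain and function either as covariates or through the propensity score, as well as the responder result.

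The cost is a short wording change, one or two extra tables, and fewer workers in the responder analysis. That loss bears most on Ohio, where about 234 completed 12-month surveys are expected.

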WA Department of Labor and Industries (DLI). The DLI State Fund provides WC insurance for over 2/3 of workers in WA (the remainder work for large self-insured companies and will be excluded due to insufficient available data). Roughly 93,000 State Fund WC claims are accepted annually. Of these, almost 20% involve time loss benefits. Of all accepted WC claims, 32% are women and 68% are men. Overall, about 21% are ≤ 24 years old at injury, 27% are 25 to 34, 24% are 35 to 44, 19% are 45 to 54, and 9% are 55 or older. Race and ethnicity are not recorded; however, in our prior research, approximately 70% of workers were white, 16% were Latino, and 13% reported other racial or ethnic backgrounds. In WA in 2016, there were over 11,000 workers with opioid prescriptions in the first 6 weeks after injury.

OH Bureau of Workers' Compensation (BWC). The BWC is the largest state-fund insurance system in the U.S. and one of the top 10 largest underwriters of WC insurance in the nation, insuring about 60% of OH's workforce. The volume of injured workers in OH is quite similar to WA. The BWC State Fund has about 90,000 accepted claims per year, and about 12% involve time loss benefits. Overall, 36% are

women and 64% are men. About 15% are \leq 24 years old at time of injury, 23% are 25 to 34, 20% are 35 to 44, 22% are 45 to 54 and 20% are 55 or older. The BWC does not collect data on race or ethnicity. In the BWC State Fund, there is an approximate annual prevalence of 20,000 opioid users.

Inclusion Criteria

Aims 1 & 2. Injured workers in OH and WA who (1) file a new accepted State Fund claim, and (2) fill at least one opioid prescription, paid for by WC, during the first 6 weeks after date of injury. The denominator for both time series described in the Analytical Methods section (Aim 1. Analysis Topic A) has the same inclusion criteria, except that criterion (2) does not apply. The same criteria—including criterion (2)—apply to the numerator for the first time series. The numerator for the second time series described is similar, except that criterion (2) is instead the presence of unsafe opioid prescribing during the subacute phase (6-12 weeks).

Aim 3 key informants. Policy makers and stakeholders who were involved in the creation and implementation of the WA or OH ORP.

Aim 3 provider in-depth interviews. Providers that had at least one patient whose opioid prescription paid for through WC had been reviewed in accordance with the state's ORP.

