OH opioid review. The OH regulations are similar to those in WA regarding best practices, but differ in approach. Rather than a “hard stop” on opioid prescription payments, an automated report identifies new opioid prescriptions beyond the acute phase. OH WC pharmacy and clinical staff review the medical record at 12 weeks to determine whether best practices were met. If not, the prescriber is notified via letter, and cases are reviewed again at 16 weeks. If best practices have still not been met, the prescriber

and worker are notified via letter that opioid coverage will end in 4 weeks. The OH program relies on retrospective chart review and communication of best practices to prescribers.

Centers of Occupational Health and Education (COHE) care delivery, in WA. The focus of the COHEs is to deliver occupational health best practices during the first 12 weeks after injury, during the transition from acute/subacute to chronic pain. The COHE delivery system has been developed over the past decade, and now approximately 50% of workers in WA receive care under these innovative arrangements. Critical elements of the COHE model include organizing care delivery on a population basis, high level executive health system support, ongoing care coordination by health service coordinators (HSCs), and stepped care management. Specific best practices include screening for psychosocial barriers to recovery using the validated Functional Recovery Questionnaire (FRQ); initiation of graded exercise; education regarding psychosocial barriers to recovery; and, more recently, a brief series of cognitive behavioral and reactivation techniques, i.e., activity coaching. COHE is a health care systems intervention, rather than a specific health care service or menu of services, that is primarily focused on improving the coordination of care at the health care community level, as well as with DLI. The COHE model consists of enhanced provider education regarding occupational health best practices and stepped-care features. Both usual care and COHE-based care in the WA workers' compensation (WC) system include the typical mix of health care services delivered for work-related injuries in Washington State, such as chiropractic care, physical therapy, evidence-based imaging services, and guideline-concordant surgery.

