Subgroup analysis will be conducted in an exploratory manner. We will include interaction terms (various covariates*state) in sub-analyses to assess whether WA PA compared to OH RR has differential outcomes for particular patient subgroups (e.g., back sprain, other MSK injuries, other injury types). We

will conduct stratified analysis for strata defined by (a) number and strength of opioid prescriptions during the acute period (0-6 weeks), and (b) continued time loss at 6 weeks.

Aim 2A

Specific aim 2A. *For injured workers in WA, examine unsafe opioid prescribing and patient-reported outcomes and work disability at 6 and 12 months for patients receiving an established, coordinated, stepped care management program during the first 12 weeks following injury plus prospective PA versus patients receiving usual care subject to PA only.*

Hypothesis 2A. *Specialized care delivered through a stepped care management program plus prospective PA will be associated with statistically significantly lower rates of unsafe opioid prescribing and improved patient outcomes compared to patients receiving usual care and PA only. [See Analysis Topics I and J]*

Aim 2A. Analysis Topic I: Compare COHE to non-COHE within WA with respect to unsafe opioid prescribing

This analysis is focused on the primary outcome for this study, unsafe opioid prescribing (defined earlier), using administrative and survey data for the full WA cohort. Our estimate is that we will have about 4,636 eligible workers in WA, and that approximately half will have an attending provider affiliated with COHE.

This analysis will test Hypothesis 2A (stated just above) with respect to unsafe opioid prescribing, using parallel analyses to those described in Analysis Topic B, and including the sensitivity analysis described in Analysis Topic C. The only adjustments are that models will include only the WA cohort, and the binary primary predictor and propensity score calculations will be based on COHE status rather than on state jurisdiction (1 for COHE, 0 for non-COHE).

Aim 2A. Analysis Topic J: Compare COHE to non-COHE within WA with respect to secondary outcomes

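### Topic I tests COHE only among workers with an opioid fill in weeks 0-6, although COHE care runs through weeks 0-12 and may affect who enters that cohort

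*Combined protocol and SAP*

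**What the plan says.** Section 4 (Inclusion Criteria, Aims 1 & 2) admits workers with a new accepted State Fund claim who "fill at least one opioid prescription, paid for by WC, during the first 6 weeks after date of injury". Section 7 (Operational Definitions for Eligibility Criteria) repeats the rule: "At least one opioid prescription during the first 6 weeks after date of injury: Based on WC pharmacy billing data".

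Topic I applies the Topic B analysis, with the Topic C sensitivity analysis, to this cohort. "The only adjustments are that models will include only the WA cohort", and that the predictor and propensity score use COHE status instead of state. The expected size is given as "Our estimate is that we will have about 4,636 eligible workers in WA", and of these "approximately half will have an attending provider affiliated with COHE". Topic J does the same in the Washington survey sample, which is recruited under the same fill criterion.

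Section 5 says of the exposure: "The focus of the COHEs is to deliver occupational health best practices during the first 12 weeks after injury". It works through provider education, care coordination and stepped care, and "now approximately 50% of workers in WA receive care under these innovative arrangements". COHE status is assigned by the provider's affiliation (Section 7, Clustering).

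Aim 2A and Hypothesis 2A are worded for injured workers in Washington, with no restriction to those who filled an opioid. Only the Topic A time series drops the fill criterion, and it is built by state, not by COHE status.

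**The concern.** For the state comparison in Aim 1, an acute fill comes before the review: Washington's payment stop applies beyond six weeks and Ohio reviews records at 12 weeks. Carried over to Aim 2A, the same criterion changes its role. COHE care begins at injury, so a fill in weeks 0-6 is observed after exposure has started and may be one of its consequences.

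If COHE changes who fills, COHE and non-COHE starters are no longer comparable, even if the injured workers behind them were. Any reduction in unsafe prescribing that comes from never starting is also invisible, because those workers are not in the data set. Section 1 names less unnecessary prescribing in the acute and subacute phases as the clearest route to preventing chronic use, so the acute half of that route is outside the test. At stake is the conclusion on Hypothesis 2A about a program that covers about half of Washington's injured workers.

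**Working it through.** **What can be reproduced.** The plan gives no power, effect size or outcome rate for Aim 2A. The cohort forecast gives 4,636 / 2 = 2,318 workers per group. Against roughly 93,000 accepted Washington claims a year (Section 4), it is 4,636 / 93,000 = 5.0%. The 2016 count of over 11,000 early fillers gives 11,000 / 93,000 = 11.8%.

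**Do the plan's figures show a COHE effect on early fills?** The COHE to non-COHE fill-rate ratio equals the odds of COHE among fillers divided by the odds of COHE among all workers. At 50% on both sides it is 1.0. Both shares are approximate. Letting each range over 45-55% gives (0.45/0.55) / (0.55/0.45) = 0.67 up to (0.55/0.45) / (0.45/0.55) = 1.49. The figures neither show nor exclude averted fills.

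**Illustration. All parameters except the 5% fill rate are assumptions.**
- Severity z is standard normal, with the same distribution in both groups.
- Non-COHE fill risk: logit = a + 1.0 z, with a = -3.37 solved so that the mean is 5%.
- Composite unsafe-prescribing risk after a fill: logit = -2.8 + 0.8 z in both groups, so COHE has no effect after starting.
- Workers without an early fill have no later event.
- COHE multiplies fill risk by (1 - r) in the affected severity range.

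Risk among starters is E[fill × risk] / E[fill]. The per-claim risk ratio is the ratio of E[fill × risk]. With r = 0.3:

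| Starts averted | Fills, COHE vs non-COHE | Risk among starters | Starter OR | Per-claim RR |
|---|---|---|---|---|
| 30% of those below +1 SD severity | 4.19% vs 5.00% | 14.4% vs 13.2% | 1.10 | 0.91 |
| 30% at every severity | 3.50% vs 5.00% | 13.2% vs 13.2% | 1.00 | 0.70 |
| 30% of those at or above +1 SD | 4.31% vs 5.00% | 12.1% vs 13.2% | 0.90 | 0.79 |

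First row as a check: (0.144/0.856) / (0.132/0.868) = 1.1, and (0.0419 × 0.144) / (0.0500 × 0.132) = 0.91. About 54% of starts lie below +1 SD, so that row averts 0.30 × 0.54 = 16% of all starts.

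**Sensitivity.** For low-severity starts, r = 0.1 gives a starter OR of 1.03 and a per-claim RR of 0.97; r = 0.5 gives 1.20 and 0.85. Setting the fill rate to 11.8% leaves the starter OR at 1.10 for r = 0.3, with a per-claim RR of 0.90.

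**Adjustment.** These ORs are crude. In the low-severity scenario with r = 0.3, adding to the logistic model a covariate that explains 25%, 50% or 75% of severity variance brings the starter OR to 1.08, 1.05 or 1.03. Perfect adjustment gives 1.00. Adjustment therefore removes the false harm but does not recover the per-claim benefit of 0.91, because the averted starters are not in the analysis.

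**The case against.** The strongest reply has four parts.

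First, the documents never say that COHE averts first prescriptions. The best practices listed in Section 5 are psychosocial screening, graded exercise, education and activity coaching, and a fill at a first visit could precede any COHE contact. This stands. The bias is conditional on an effect that the plan does not measure.

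Second, the planned analysis is adjusted. Topic B covariates include injury type, comorbidity and, if available, pre-injury opioid prescriptions. Topic C adds survey covariates such as pain intensity and function, with full use of propensity scores. This stands in part: adjustment would shrink the selection bias. But several candidates (early utilization, time to first opioid, the 4-6 week survey) are measured after COHE care begins, and restriction to common support does not bring back workers who never filled.

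Third, progression among starters is a coherent question. Topic B describes its composite outcome as assessing the move from early opioid therapy to longer-term unsafe prescribing. This also stands. A reader might infer that the starter analysis is invalid and should be replaced or demoted; the documents do not support that. They support labelling it as conditional, because the aim and hypothesis are worded more widely.

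Fourth, the contrast with Aim 1 is not absolute. The Clustering section allows that review may change providers' practice for other patients. That qualifies the contrast, but does not affect the overlap of COHE with weeks 0-6.

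**Conclusion.** The design point holds. Cohort entry for Aim 2A comes after exposure can begin, and no planned Aim 2A analysis uses all claims or compares early fills by COHE status. If COHE averts early fills and has no effect after starting, the starter-only comparison misses some or all of the benefit. At 30% aversion the illustration gives starter ORs from 0.90 to 1.10 against per-claim RRs from 0.70 to 0.91.

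A reader might infer that the planned estimate is biased toward harm or has the wrong sign. The documents do not support that. A reversal needs two things the plan does not state: that COHE averts early fills, and that the averted fills are mainly lower-risk. Uniform aversion hides the benefit, and aversion of higher-risk fills understates it. If COHE averts no fills, this mechanism produces no bias. The sizes rest on assumed severity and risk models, on unadjusted comparisons, and on no later events without an early fill. Aim 2A is a secondary comparison, so this is a worthwhile correction and not a threat to the primary analysis.

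**What to change.** For the administrative outcomes in Aim 2A, add an analysis over all accepted adult Washington State Fund claims in the cohort injury year: the Topic A denominator with no fill criterion and with the cancer exclusion kept. Assign COHE status by first attending provider, use covariates fixed at injury, and keep the same composite outcome. Report weeks 0-6 opioid fill rates by COHE status, which shows directly whether entry differs between the groups.

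Keep the starter analysis in Topic I, and state that its conclusion is conditional on having filled an early opioid prescription. State the same for Topic J. Its survey outcomes cannot be extended to all claims, because only fillers are surveyed.

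Cost: new plan wording and a wider Washington extract. Topic A already covers the cohort's injury dates but uses pharmacy data only up to three months after injury. The addition needs 12 months of pharmacy data, attending provider and covariates on about 93,000 claims. That is 93,000 / 11,000 = 8.5 times the starter cohort on the 2016 count, or 93,000 / 4,636 = 20 times on the forecast. The plan describes the Washington administrative data as virtually complete. The outcome will be rarer per claim (about 0.05 × 0.132 = 0.7% in the illustration), and confounding by injury mix will remain.
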